### **Electronic Serious Adverse Event (eSAE) Reporting Process**

Site personnel record all SAE data in the eCRF database and from there transmit the SAE information to Nektar Drug Safety within 24 hours of the Investigator's knowledge of the event. Detailed instructions can be found in the eCRF completion guidelines.

If for any reason it is not possible to record the SAE information electronically, that is, the eCRF database is not functioning, record the SAE on the paper SAE reporting form and submit within 24 hours of the Investigator's knowledge of the event to Nektar Therapeutics Drug Safety via email or Safety Fax as provided in the [List of Study Contacts](#) at the beginning of this protocol.

As soon as it is possible to do so, any SAE reported via paper must be transcribed into the eCRF Database according to instructions in the eCRF completion guidelines. If an SAE has been reported via a paper form because the eCRF database has been locked, no further action is necessary.

Copies of hospital case reports, autopsy reports, and other documents are also to be submitted by email or fax when requested and applicable. Transmission of such documents should occur without personal patient identification, maintaining the traceability of a document to the patient identifiers. Additional information may be requested to ensure the timely completion of accurate safety reports. Any medications necessary for treatment of the SAE, AESI, or ECIs must be recorded onto the concomitant medication section of the patient's eCRF and the event description section of the SAE form.

All SAEs will be followed as described in Section [10.8](#).

Reporting of SAEs to the IRB/IEC will be done in accordance with the standard operating procedures (SOPs) and policies of the IRB/IEC. Adequate documentation must be provided to Nektar Therapeutics, showing that the IRB/IEC was properly notified. Serious AEs will be reported by Nektar Therapeutics or designee to the Regulatory Authorities, per local regulations.

### 10.8 Serious AE Follow-up

All study treatment-related SAEs that have not resolved by the last Follow-Up Visit (Section 6.3) will be followed until any of the following occur (whichever comes first):

- The event resolves.
- The event has stabilized.
- The event returns to baseline, if a baseline value is available.
- It is unlikely that any additional information can be obtained (eg, patient or healthcare practitioner refuses to provide additional information; lost to follow-up after demonstration of due diligence with follow-up efforts [as defined in Section 6.2.7]).
- The patient dies or is lost to follow-up (as defined in Section 6.2.7).

All ongoing SAEs assessed as unrelated to study drug(s) will be followed until resolution or until the last Follow-Up Visit (Section 6.3), whichever is earlier. In the case where an unrelated SAE has not completely resolved by the last Follow-Up Visit, the final outcome of these unrelated ongoing SAEs will be captured as “Not Recovered/Not Resolved” or “Recovering/Resolving”, whichever is applicable.

### 10.9 Disease Progression and Death due to Disease Progression– Not Reportable as an AE or SAE

It is anticipated that during this study a proportion of patients will experience disease recurrence prior to study discontinuation. In some patients this may result in hospitalization or death. Such events leading to hospitalization or death of a study patient are typically considered “serious,” requiring submission of an SAE report. However, because disease recurrence is an endpoint for this study, reporting the term “disease recurrence” as either an AE or SAE is not necessary. Signs and symptoms with no principal clinical manifestation related to disease recurrence, may be considered as “disease recurrence” without a requirement to report it as an AE or SAE.

For all SAEs assessed as clinical manifestations associated with fatal disease progression, the following criteria will apply:

- Seriousness Criteria cannot equal Death
- Severity cannot equal Grade 5
- Outcome = Ongoing at time of Death

Deaths that are attributed solely to disease recurrence by the Investigator should not be reported as SAEs.

However, if there are separate identifiable clinical manifestations of the disease recurrence that the Investigator is unsure that the events are attributed solely to disease recurrence, for example, pleural effusion or weight loss, these manifestations are reportable as AEs. Such an event should be recorded on the AE CRF and, if the event meets any of the “serious” criteria, it must also be reported on the SAE form.

#### **10.10 Disease-Related Events and/or Disease-Related Outcomes Not Qualifying as AEs or SAEs**

Specifically, the suspected/actual events covered in this exception include any event that is disease progression of the cancer under study.

The Sponsor will ensure that unblinded aggregated efficacy endpoint events and safety data are monitored to safeguard the patients in the study.

#### **10.11 Immune-Mediated Adverse Events**

Immune-mediated AEs (also referred to as immune-related AEs [irAEs] in this document) are AEs consistent with an immune-mediated mechanism or immune-mediated component for which non-inflammatory etiologies (eg, infection or tumor progression) have been ruled out.

Immune-mediated AEs can include events with an alternate etiology which were exacerbated by the induction of autoimmunity. Investigators should use clinical judgment characterizing an AE as immune-mediated, including the requirement for steroid treatment, and are encouraged to rule out neoplastic, infectious, metabolic, toxic, or other etiologies to the extent possible, before characterizing an event as immune-mediated. Information supporting the assessment of immune-mediated AEs will be collected on the CRF.

#### **10.12 Adverse Events of Special Interest for Bempegaldesleukin**

Selected serious and nonserious AEs for bempegaldesleukin are also known as adverse events of special interest (AESIs) and must be reported to the Sponsor.

An AESI for bempegaldesleukin in this study is CVA, which should follow the AE grading criteria (see Section 10.3) and the standard seriousness definition (see Section 10.6). All AESIs occurring in both arms are required to follow the timeline for SAE reporting (within 24 hours as described in Table 11 and Section 10.7) in order to remove potential bias from dissimilar reporting between the treatment arms. The purpose of such reporting criteria is to obtain adequate information for proper clinical assessment of CVA events. Patients with recurrent and metastatic disease are known to have a higher risk for CVA.

CVA Management Guidelines for the study are provided in [Appendix 2](#).

### 10.13 Potential Drug-Induced Liver Injury for Bempegaldesleukin

For patients in Arm A receiving bempegaldesleukin, wherever possible, timely confirmation of initial liver-related laboratory abnormalities should occur prior to the reporting of a potential drug-induced liver injury (DILI) event according to the elevated liver enzyme criteria defined in Section 10.14. For patients in Arm A receiving bempegaldesleukin, all occurrences of potential DILIs meeting the criteria defined in Section 10.14 must be assessed for causal etiology with concomitant medications and/or for individual study drug association and reported as SAEs (see Section 10.7 for reporting details).

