### 4.2 Secondary Objectives and Endpoints

The secondary objectives and endpoints listed below involve comparison of bempegaldesleukin plus pembrolizumab versus pembrolizumab monotherapy in first-line patients with recurrent or metastatic HNSCC and positive PD-L1 expression (defined by CPS  $\geq$  1) who have not received prior therapy for the treatment of recurrent or metastatic HNSCC:

Secondary Objective	Endpoint
To compare progression-free survival (PFS).	PFS, defined as the time from randomization to the first documented disease progression (per RECIST 1.1 by BICR) or death due to any cause, whichever occurs first.
To compare time to deterioration in global health status/quality of life, pain, and swallowing.	The time from baseline to a $\geq$ 10-point decrease from baseline with confirmation by the subsequent visit of a $\geq$ 10-point deterioration from baseline in: 
 
Global health status/quality of life assessment based on the global health status/quality of life scales of the European Organization for Research and Treatment of Cancer (EORTC) Quality of Life Questionnaire-Core 30 (QLQ-C30).
 
Pain based on the pain multi-item scales of EORTC QLQ head and neck cancer specific module (EORTC QLQ-H&N35).
 
Swallowing based on the swallowing multi-item scales of EORTC QLQ-H&N35.
 

To compare mean change from baseline in global health status/quality of life.	Mean change from baseline in global health status/quality of life scales of EORTC QLQ-C30.
To compare the overall safety and tolerability.	Safety will be based on assessments of treatment-emergent adverse events (AEs) and serious AEs (SAEs).

[Redacted]

[Redacted]	[Redacted]
[Redacted]	[Redacted]
[Redacted]	[Redacted]
[Redacted]	[Redacted]
[Redacted]	[Redacted]
[Redacted]	[Redacted]
[Redacted]	[Redacted]
[Redacted]	[Redacted]
[Redacted]	[Redacted]
[Redacted]	[Redacted]
[Redacted]	[Redacted]
[Redacted]	[Redacted]
[Redacted]	[Redacted]
[Redacted]	[Redacted]
[Redacted]	[Redacted]
[Redacted]	[Redacted]
[Redacted]	[Redacted]

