**Table 11: Reporting Time Periods and Time Frames for Adverse Events and Other Reportable Safety Events**

Type of Event	Reporting Time Period: Consent to Randomization/ Allocation	Reporting Time Period: Randomization/ Allocation through Protocol-specified Follow-up Period a	Reporting Time Period: After the Protocol-specified Follow- up Period	Time Frame to Report Event and Follow-up Information to Sponsor
NSAE	Report if: - due to protocol-specified intervention - causes exclusion	Report all	Not required	Per data entry guidelines
SAE including Cancer b and Overdose	Report if: - due to protocol-specified intervention - causes exclusion	Report all	Report if: - drug/vaccine related. (Follow ongoing to outcome)	Within 24 hours of learning of event
Pregnancy/ Lactation Exposure	Report if: - patient has been exposed to any protocol-specified intervention (eg, procedure, washout)  Exception: A positive pregnancy test at the time of initial screening is not a reportable event.	Report all	Previously reported – Follow to completion/termination; report outcome	Within 24 hours of learning of event
ECI (require regulatory reporting)	Report if: - due to intervention - causes exclusion	Report - potential DILI - require regulatory reporting	Not required	Within 24 hours of learning of event
ECI (do not require regulatory reporting)	Report if: - due to intervention - causes exclusion	Report - non-DILI ECIs and those not requiring regulatory reporting	Not required	Within 5 calendar days of learning of event
AESI (require regulatory reporting)	Report if: - due to intervention - causes exclusion	Report all	Not required	Within 24 hours of learning of event

Abbreviations: AESI = adverse event of special interest; DILI = drug-induced liver injury; ECI = Event of Clinical Interest; NSAE = nonserious adverse event; SAE = serious adverse event.

- a. Follow-up period includes:
  - Follow-Up Visit 1: reported until 30 days after the last dose of all study drug(s) and
  - Follow-Up Visit 2: reported only for SAEs until 90 days after the last dose of all study drug(s).
- b. A new cancer that is not a condition of the study indication.

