### 10.14 Events of Clinical Interest for Pembrolizumab

Selected serious and nonserious AEs for pembrolizumab are also known as events of clinical interest (ECIs) and must be reported to the Sponsor.

Events of clinical interest for pembrolizumab in this study include:

1. An overdose of Sponsor's product, as defined in Section 10.15.
2. An elevated AST or ALT laboratory value that is greater than or equal to  $3 \times$  ULN and an elevated total bilirubin laboratory value that is greater than or equal to  $2 \times$  ULN and, at the same time, an alkaline phosphatase laboratory value that is less than  $2 \times$  ULN, as determined by way of protocol-specified laboratory testing or unscheduled laboratory testing.\*

\*Note: These criteria are based on available regulatory guidance documents. The purpose of the criteria is to specify a threshold of abnormal hepatic tests that may require an additional evaluation for an underlying etiology.

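### The same liver laboratory pattern is an automatic SAE in Arm A but an SAE only by judgment in Arm B, so the hepatic part of the between-arm SAE comparison lacks one definition

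*Protocol*

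**What the plan says.** **Arm A.** Protocol Section 10.13 states: "For patients in Arm A receiving bempegaldesleukin, all occurrences of potential DILIs meeting the criteria defined in Section 10.14 must be assessed" for causal etiology and then "reported as SAEs (see Section 10.7 for reporting details"). The same section asks that initial liver abnormalities be confirmed before reporting, wherever possible. That step is also written for Arm A patients receiving bempegaldesleukin only.

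**Arm B.** Section 10.14 lists the same laboratory pattern among the pembrolizumab ECIs, "as determined by way of protocol-specified laboratory testing or unscheduled laboratory testing". It describes the category in these words: "Selected serious and nonserious AEs for pembrolizumab are also known as events of clinical interest (ECIs) and must be reported to the Sponsor". Nothing there makes the pattern an SAE. An Arm B case reaches that status only through the general definition in Section 10.6, for example as an important medical event in the investigator's judgment.

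**Table 11.** Potential DILI sits in an ECI row that is not arm-specific and is separate from the SAE row. The entry is "Report - potential DILI - require regulatory reporting", with a 24-hour time frame.

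**Use of SAEs.** Section 4.2 includes a comparison of overall safety and tolerability between the arms: "Safety will be based on assessments of treatment-emergent adverse events (AEs) and serious AEs (SAEs"). The synopsis (Statistical Methods, Safety) summarizes SAE incidence descriptively by arm.

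**The concern.** One set of laboratory values is serious by rule in one arm and serious by discretion in the other. The trial is open-label (Section 3.2.1), so that discretion is exercised with the arm known. If the two arms had exactly the same frequency of the pattern, Arm A could still show more hepatic SAEs.

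This falls where a real difference is plausible. Section 2.2.1 names transaminase elevation as an identified bempegaldesleukin risk. The DMC looks at safety about twice a year (Section 2.2.4). Readers of a by-arm SAE table would need to know how much of any hepatic excess comes from the reporting rule.

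**Working it through.** The plan gives no figure to reproduce. The check sets the rules side by side and then bounds the effect.

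**Rules for the same laboratory pattern**

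| Feature | Arm A receiving bempegaldesleukin | Arm B |
|---|---|---|
| Laboratory criteria | Section 10.14 | Section 10.14 |
| Notice to sponsor | 24 hours | 24 hours (Table 11, ECI row) |
| Confirmation before reporting | Asked for where possible (10.13) | Not stated |
| Seriousness | Always an SAE (10.13) | SAE only if Section 10.6 is judged met |

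Criteria and notification time match; seriousness and confirmation do not. One qualification: a Table 11 footnote limits reporting from 30 to 90 days after the last dose to SAEs. The match is therefore clear only up to day 30.

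**Inputs**
- n = 250 per arm (synopsis, planned number of patients), taking all as dosed.
- r = true proportion of patients with the pattern, equal in both arms. The documents give no rate; 0.5% to 3% is an assumption.
- f = fraction of Arm B cases classed as serious by judgment. Not given; range 0 to 1.

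**Formula.** Cases counted as SAEs are n x r in Arm A and n x r x f in Arm B. The artificial difference in proportions is r - r x f = r x (1 - f).

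| r | Arm A cases (250 x r) | f = 0 | f = 0.5 | f = 0.9 | f = 1 |
|---|---|---|---|---|---|
| 0.5% | 1.25 | 0.5 points | 0.25 | 0.05 | 0 |
| 1% | 2.5 | 1.0 | 0.5 | 0.1 | 0 |
| 2% | 5 | 2.0 | 1.0 | 0.2 | 0 |
| 3% | 7.5 | 3.0 | 1.5 | 0.3 | 0 |

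**Dilution at patient level.** A patient who has another SAE is counted anyway. If a share s of these patients has one, the difference becomes r x (1 - f) x (1 - s). For illustration only, take s = 0.447, the SAE proportion in the bempegaldesleukin plus nivolumab doublet (Section 2.1.3.2.2), and assume independence. At r = 1% and f = 0 this gives 1.0 x (1 - 0.447) = 0.55 points. At r = 3% it gives 3.0 x 0.553 = 1.66 points.

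The Arm A confirmation step may remove some Arm A reports and shrink the difference further. So r x (1 - f) is an upper bound.

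**The case against.** The strongest reply is that the mismatch is small and recoverable. Most of it stands.

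- **Arm B cases are not confined to ECI status.** ECIs may be serious. Table 6 also calls for withholding or discontinuing treatment and giving corticosteroids for immune-related liver abnormalities of this order, so many Arm B cases could be judged important medical events. If all were, f = 1 and the difference is zero.
- **A reader might infer that a true hepatic excess could not be told apart from the reporting rule.** The documents do not support that. The criterion is purely laboratory-based, and AST, ALT, alkaline phosphatase and bilirubin are in the central chemistry panel (Appendix 1A), drawn before dosing each cycle in both arms (Table 1). Laboratory abnormalities are also part of the by-arm safety summary.
- **A reader might infer that Section 10.12 removes exactly this asymmetry for cerebrovascular accident.** It does not. Its stated purpose, "in order to remove potential bias from dissimilar reporting between the treatment arms", attaches to the reporting timeline, and seriousness is left to the standard definition. On timeline, Table 11 already treats potential DILI alike in both arms.
- **The pattern may be rare.** Section 6.5.1.1.2 says bempegaldesleukin transaminase elevations usually occur without raised bilirubin.
- **The safety tabulations cannot be fully seen.** Protocol text between the PFS analysis in Section 11.5.2 and Section 11.9.1 is redacted, so a planned handling of hepatic events cannot be ruled out.

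None of this supplies a common seriousness rule. Section 10.13 still fixes the classification in one arm and leaves it open in the other.

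**Conclusion.** The point holds as a small protocol-design flaw. For one laboratory pattern the arms have different SAE definitions, and the effect runs against Arm A. Its size is at most r x (1 - f), or 0 to 3 percentage points if r is 0.5 to 3%, and smaller at patient level. Both r and f are assumptions, as is an equal true rate.

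The defect lies in seriousness classification, not in whether cases come to notice. Safety is descriptive, and no OS or ORR test is touched. It would be wrong to infer that reported results are biased: SAP Section 2.0 records one patient enrolled and treated, with listings and no summary, so no between-arm SAE comparison will be made. Confidence is high for the mismatch in wording and lower for its practical effect.

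**What to change.** Reconcile Sections 10.13, 10.14 and Table 11 so that one seriousness classification and one confirmation step for this pattern apply to both arms. Either every case is an SAE in both arms, or every case is an ECI in both with SAE status set by Section 10.6. State also whether the rule covers Arm A patients who continue on pembrolizumab alone, since Section 10.13 speaks of those receiving bempegaldesleukin. With a common rule the artificial difference is zero for any r, provided the true rates are equal.

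If the Arm A rule must stay, present the by-arm SAE summary with and without events serious only through Section 10.13. Add a by-arm comparison of laboratory-defined potential DILI from the central chemistry already collected. Central values on the common schedule are preferable because Arm A also has local liver tests before each bempegaldesleukin dose (Appendix 1B).

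The cost is a wording change plus either a few extra SAE forms in Arm B or one extra table.

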### 10.14 Events of Clinical Interest for Pembrolizumab

Selected serious and nonserious AEs for pembrolizumab are also known as events of clinical interest (ECIs) and must be reported to the Sponsor.

Events of clinical interest for pembrolizumab in this study include:

1. An overdose of Sponsor's product, as defined in Section 10.15.
2. An elevated AST or ALT laboratory value that is greater than or equal to  $3 \times$  ULN and an elevated total bilirubin laboratory value that is greater than or equal to  $2 \times$  ULN and, at the same time, an alkaline phosphatase laboratory value that is less than  $2 \times$  ULN, as determined by way of protocol-specified laboratory testing or unscheduled laboratory testing.\*

\*Note: These criteria are based on available regulatory guidance documents. The purpose of the criteria is to specify a threshold of abnormal hepatic tests that may require an additional evaluation for an underlying etiology.

### 10.15 Treatment of Overdose

For this study:

- For pembrolizumab, an overdose will be defined as any dose of 1000 mg pembrolizumab or greater.
- For bempegaldesleukin, an overdose is defined as the accidental or intentional administration of any dose of a product that is considered both excessive and medically important.

No specific information is available on the treatment of overdose of pembrolizumab or bempegaldesleukin. In the event of overdose, the patient should be observed closely for signs of toxicity. Appropriate supportive treatment should be provided if clinically indicated.

Overdoses that meet the regulatory definition of SAE will be reported as an SAE (see Section 10.6). All instances of accidental overdose and/or dosing errors should be reported on the Dosage Administration Record CRF.

## 10.16 Pregnancy Tests/Pregnancy

### 10.16.1 Pregnancy Tests

Serum or urine pregnancy tests will be performed on women of childbearing potential (WOCBP) according to the Schedule of Events (Section 1.2). Pregnancy testing (urine or serum as required by local regulations) should also be conducted 120 days after the last dose of study drug.

Pregnancy testing requirements for study inclusion are described in Section 5.1.

Pregnancy testing (urine or serum as required by local regulations) should be conducted prior to every cycle (q3w) or more frequently if required by local regulations.

Additional serum or urine pregnancy tests may be performed, as determined necessary by the investigator or required by local regulation, to establish the absence of pregnancy at any time during the subject's participation in the study.

Urine pregnancy tests should have a highly sensitive pregnancy test. A negative pregnancy test result must be obtained before the administration of the study drug(s).

A pregnancy test does not need to be performed on women who are postmenopausal (see Appendix 5) for at least 1 year or surgically sterile for at least 3 months before signing the ICF.

### 10.16.2 Pregnancy

#### 10.16.2.1 Pregnancy and Lactation in Female Patients

The Sponsor must be notified immediately without undue delay, under no circumstances later than 24 hours following knowledge of the initial report and any follow-up reports of a female patient becoming pregnant or breastfeeding during the course of the study and for 120 days after the last dose of study drug or 30 days after cessation of study drug if the patient initiates a new anticancer treatment for female patients. All reports should be submitted via the Pregnancy Notification Form. Pregnancy, although reportable, is not considered an AE/SAE unless a female patient experiences signs or symptoms of pregnancy complications; however, the contact information for pregnancy reporting is the same as for SAE reporting and listed in Section 10.7. Female patient(s) who become pregnant will be followed until the outcome of the pregnancy is known. Pregnancy follow-up should describe the outcome of the pregnancy, including any voluntary or spontaneous termination, details of the birth, and the presence or absence of any congenital abnormalities or birth defects in the offspring. Pregnancy outcomes of ectopic pregnancy, spontaneous abortion, missed abortion, benign hydatidiform mole, blighted ovum, fetal death, intrauterine death, miscarriage, and stillbirth must be reported as serious events (Important Medical Events). If the pregnancy continues to term, the outcome (health of infant) must also be reported.

If a female patient becomes pregnant, administration of the study drug(s) must be discontinued immediately.

